8.1.1.3. Immune-Related RECIST (irRECIST)

Immunotherapeutic agents such as pembrolizumab may produce antitumor effects by potentiating endogenous cancer-specific immune responses. The response patterns seen with such an approach may extend beyond the typical time course of responses seen with cytotoxic agents, and can manifest a clinical response after an initial increase in tumor burden or even the appearance of new lesions. Standard RECIST may not provide an accurate response assessment of immunotherapeutic agents such as pembrolizumab. Therefore, for Study JVDF, RECIST 1.1 will be adapted to account for the unique tumor response characteristics seen with treatment of pembrolizumab (immune-related RECIST [irRECIST]). irRECIST will be applied as detailed below for treatment-related decisions, and the resulting data will be included in the clinical database.

If radiologic imaging verifies initial progressive disease (PD), tumor assessment should be repeated approximately 4 weeks later in order to confirm PD with the option of continuing study treatment per below while awaiting radiologic confirmation of progression.

If repeat imaging shows < 20% target lesion compared to nadir, stable or improved previous new lesion (if identified as cause for initial PD), and stable/improved non-target disease (if identified as cause for initial PD), treatment may be continued / resumed.

If repeat imaging confirms PD due to any of the scenarios listed below, patients will be discontinued from study treatment. In determining whether or not the tumor burden has increased or decreased, site study team should consider all target lesions as well as non-target lesions (see Site Guidance Document for RECIST/irRECIST).

Scenarios where PD is confirmed at repeat imaging:

- Target lesions remains $\geq 20\%$ and at least 5-mm absolute increase compared to nadir.
- Non-target disease resulting in initial PD is worse (qualitative).
- New lesion resulting in initial PD is worse (qualitative).
- Additional new lesion(s) since last evaluation

In patients who have initial evidence of radiological PD, it is at the discretion of the treating physician whether to continue a patient on study treatment until repeat imaging is obtained. This clinical judgment decision should be based on the patient's overall clinical condition, including performance status, clinical symptoms, and laboratory data. Patients may receive study treatment while waiting for confirmation of PD if they are clinically stable as defined by the following criteria:

- absence of signs and symptoms indicating disease progression
- no decline in ECOG performance status
- absence of rapid progression of disease

- absence of progressive tumor at critical anatomical sites (for example, cord compression) requiring urgent alternative medical intervention

When feasible, patients should not be discontinued from study treatment until progression is confirmed by the second radiographic exam. This allowance to continue treatment despite initial radiologic progression takes into account the observation that some patients can have a transient tumor flare in the first few months after the start of immunotherapy, but with subsequent disease response. Patients who are deemed clinically unstable are not required to have repeat imaging for confirmation of PD.

[Table JVDF.6](#) summarizes the guidance for imaging and treatment after the first radiologic evidence of PD.

Table JVDF.6. Imaging and Treatment after First Radiologic Evidence of Progressive Disease

	Clinically Stable		Clinically Unstable	
	Imaging	Treatment	Imaging	Treatment
First radiologic evidence of PD	Repeat imaging approximately 4 weeks later at site to confirm PD	May continue study treatment at the investigator's discretion while awaiting confirmatory scan	Repeat imaging approximately 4 weeks later to confirm PD, per investigator discretion only	Discontinue treatment
Repeat scan confirms PD	No additional imaging required	Discontinue treatment	No additional imaging required	N/A
Repeat scan shows SD, PR, or CR	Continue regularly scheduled imaging assessments every 6 weeks	Continue study treatment at the investigator's discretion	Continue regularly scheduled imaging assessments every 6 weeks	May restart study treatment if condition has improved and/or clinically stable per Investigator's discretion

Abbreviations: CR = complete response; N/A = not applicable; PD = progressive disease; PR = partial response; SD = stable disease.

NOTE: Discontinuation of study treatment may be considered for patients who have attained a confirmed CR that have been treated for at least 24 weeks with study treatment and had at least 2 treatment cycles beyond the date when the initial CR was declared.

In determining whether or not the tumor burden has increased or decreased, study site investigators should consider all target lesions as well as non-target lesions (see Procedure Manual). Patients that are deemed clinically unstable are not required to have repeat tumor imaging for confirmation. If radiologic progression is confirmed by subsequent scan, then the patient will be discontinued from study treatment. If radiologic progression is not confirmed,

then the patient should resume or continue trial treatment and have their next tumor imaging according to the protocol schedule of every 6 weeks (\pm 7 days).

8.1.2. *Efficacy Assessments during Postdiscontinuation Follow-Up*

Postdiscontinuation follow-up during the study period will be conducted per the Time and Events Table ([Attachment 1](#)).

Tumor assessments may continue for patients who are withdrawn from the study for reasons other than disease progression every 6 to 12 weeks depending on standard of care.

8.1.3. *Efficacy Measures*

The objective response rate (ORR) is the proportion of enrolled patients who have received any amount of either study drug, have at least 1 postbaseline tumor image, and achieve a best overall response of complete response (CR) or partial response (PR). The ORR will be assessed based on RECIST 1.1 (Eisenhauer et al. 2009) and irRECIST.

Time-to-response (TTR) is the time from the date of first study treatment until the first evidence of a confirmed CR or PR, as defined in Section [8.1.1.3](#).

Duration of response (DoR) is defined only for responders (patients with a confirmed CR or PR). It is measured from the date of first evidence of a confirmed CR or PR to the date of objective progression or the date of death due to any cause, whichever is earlier. If a responder is not known to have died or have objective progression as of the data inclusion cutoff date, DoR will be censored at the date of the last complete objective progression-free disease assessment.

Disease Control Rate (DCR) is defined as the proportion of enrolled patients who have a best overall response of CR, PR, or stable disease (SD).

Progression-free survival (PFS) is defined as the time from the date of first study treatment until the date of the first observed radiographically documented PD or death due to any cause, whichever is earlier. The censoring is taken in the following order:

- if a patient does not have a complete baseline disease assessment, then the PFS time will be censored at the enrollment date, regardless of whether or not objectively determined disease progression or death has been observed for the patient; otherwise,
- if a patient is not known to have died or have objective progression as of the data inclusion cutoff date for the analysis, the PFS time will be censored at the last complete objective progression-free disease assessment date.

TTR, DoR, DCR, and PFS will be assessed based on RECIST 1.1. Exploratory analysis of TTR, DoR, and PFS may be conducted using irRECIST.

Overall survival (OS), including 1- and 2- year survival rates, is determined from the date of first study treatment until death due to any cause. If the patient was alive at the data inclusion cutoff date for the analysis (or was lost to follow-up), OS will be censored on the last date the patient was known to be alive.

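### Protocol 8.1.1.3: non-target progression first seen at the repeat scan does not confirm PD, although Attachment 6 scores that scan PD and the SAP caption would count it as confirmation

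*Protocol*

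**What the plan says.** Protocol 8.1.1.3 asks for repeat imaging about 4 weeks after a first radiologic PD and gives two rules for reading it.

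- **The confirmed-PD list.** Treatment must stop if any of four findings is present: target lesions still at least 20% and at least 5 mm above nadir; "Non-target disease resulting in initial PD is worse (qualitative"; a causal new lesion that is worse; or "Additional new lesion(s) since last evaluation". The last item applies whatever caused the first PD. The non-target item does not.
- **The continue sentence.** It starts "If repeat imaging shows < 20% target lesion compared to nadir, stable or improved previous new lesion" (again only if causal) and ends "stable/improved non-target disease (if identified as cause for initial PD), treatment may be continued / resumed".

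If progression is not confirmed, the closing paragraph of the section says "then the patient should resume or continue trial treatment and have their next tumor imaging". Table JVDF.6 provides two outcomes for the repeat scan: it confirms PD, or "Repeat scan shows SD, PR, or CR". The section introduces all this by saying that "RECIST 1.1 will be adapted to account for the unique tumor response characteristics seen with treatment of pembrolizumab". It also says that "study site investigators should consider all target lesions as well as non-target lesions (see Procedure Manual", and it refers sites to a Site Guidance Document.

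Attachment 6 scores any time point with unequivocal progression of existing non-target lesions as PD, whatever the target lesions show.

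SAP 5.2.1.5 applies irRECIST as the protocol details it. It dates immune-related PD (irPD) at the first PD if that is confirmed, and otherwise at the second PD. The captions to its two graphic examples equate confirmed with PD at consecutive scans, and not confirmed with PD at non-consecutive scans.

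**The concern.** A disease that spreads to a further compartment at the repeat scan is hard to call unconfirmed progression. Yet the list does so whenever the first PD came from target lesions or a new lesion and the non-target disease only now progresses. Response is read locally by the investigator, so the written rule is what keeps sites consistent. Here a site that follows the list, one that scores the scan by Attachment 6, and one that looks for a row in Table JVDF.6 can reach different answers.

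Two things are at stake: whether treatment must stop, and which date enters the exploratory irRECIST analyses that use irPD.

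**Working it through.** No sample size, power or alpha figure depends on this rule, so there is no plan figure to reproduce. The check applies the rules to one record and then to every logical type of repeat scan.

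**1. One record (illustrative measurements).** With first treatment on day 1, the 6-week imaging schedule (±7 days) falls on days 43 and 85. Nadir sum 100 mm. Day 43: 125 mm, +25% and +25 mm, so first PD, from target lesions only. Repeat scan 28 days later, day 43 + 28 = 71: 115 mm, (115 − 100)/100 = +15%; no new lesion; unequivocal non-target progression for the first time.

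| Rule | Reading of the day 71 scan |
|---|---|
| 8.1.1.3 list, target item | not met (+15%) |
| 8.1.1.3 list, non-target item | not met (non-target disease did not cause the first PD) |
| 8.1.1.3 list, two new-lesion items | not met |
| 8.1.1.3 continue sentence | met |
| 8.1.1.3 default | not confirmed, so treatment goes on |
| Attachment 6 | PD |
| Table JVDF.6 | no row: not SD, PR or CR, and not confirmed by the list |
| SAP 5.2.1.5 captions | PD at consecutive scans, so confirmed |

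**2. Effect on the irPD date.** If confirmed, irPD is day 43. If not confirmed, it is the second PD: day 71 if the repeat scan itself is that PD, a shift of 71 − 43 = 28 days. If the second PD is taken at or after the next scheduled scan, the shift is 85 − 43 = 42 days or more.

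**3. All repeat-scan types.** These are logical cells, not patient frequencies. Cross the single cause of first PD (target, non-target, new lesion), target change at repeat (<20%; ≥20% but <5 mm; ≥20% and ≥5 mm), non-target status (stable or worse), additional new lesion (no, yes) and, where a new lesion was the cause, its status (stable or worse):

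- Target cause: 3 × 2 × 2 = 12. Non-target cause: 12. New-lesion cause: 3 × 2 × 2 × 2 = 24. Total 48.
- List only: 33. Continue sentence only: 5. Both: 5. Neither: 5.
- As written, 33 + 5 = 38 cells are confirmed and 5 + 5 = 10 are not.
- Of the 10 not confirmed, 4 have first non-target progression: 2 with target <20%, where the continue sentence is met, and 2 with target ≥20% but <5 mm.
- With the missing list item, 38 + 4 = 42 are confirmed and 10 − 4 = 6 are not.

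**4. The other two mismatches between list and sentence.**

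- The 5 cells that meet both rules all have an additional new lesion, which the continue sentence does not mention. The list's wording is mandatory and the sentence's is permissive, so treatment stops.
- The 5 cells that meet neither rule arise because the sentence omits the 5-mm term. This requires a nadir sum below 5/0.20 = 25 mm. Example: nadir 20 mm, first PD 26 mm (+30%, +6 mm), repeat 24 mm (+20%, +4 mm). Attachment 6 needs both 20% and 5 mm, so with nothing else progressing this scan is SD or PR, and the Table JVDF.6 continuation row covers it. That settles 3 of the 5 cells. The other 2 have first non-target progression and are settled only by the default for unconfirmed PD.

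**The case against.** The strongest reply is that the limit is deliberate. It appears in both the list and the continue sentence, and the section says that RECIST 1.1 is being adapted, so some departure from Attachment 6 is expected. That may be so. But the protocol does not say that non-target progression first seen at the repeat scan is excluded, and the section tells sites to weigh all non-target lesions. Intent would also leave Table JVDF.6 without a row and the SAP captions out of step.

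A second reply is that the SAP figures, the Site Guidance Document and the Procedure Manual, none of which was available, may settle the matter. The SAP's operative bullets do speak of confirmed and unconfirmed PD and the SAP defers to the protocol, so the captions are the weaker text. This stands as a limit on confidence.

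A third is that the situation is uncommon. Attachment 6 itself describes unequivocal non-target progression as rare, and the record needs several findings on one scan. SAP 5.3.10 also lists both the initial and the irRECIST progression, so a discrepancy would be visible. This stands and bears on severity.

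Three stronger readings are tempting, and the documents do not support them:

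- **That the rules are contradictory or undefined.** Every one of the 48 cells has an outcome once the mandatory wording, Attachment 6 with Table JVDF.6, and the default are applied. The additional-new-lesion overlap and the 5-mm gap are drafting mismatches only.
- **That patients with advancing disease are held on treatment.** Protocol 7.1 lets the investigator stop treatment at any time.
- **That the immune-related response rate is inflated.** It could change only if a later response fell within what the SAP calls the confirmation stage, which it does not define.

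**Conclusion.** The concern holds in a narrow form. Under the Protocol 8.1.1.3 list, non-target progression that first appears at the repeat scan, after a first PD from target lesions or a new lesion, leaves PD unconfirmed. Attachment 6 calls the scan PD, Table JVDF.6 does not provide for it, and the SAP caption would call it confirmed. In logical terms this is 4 of 48 repeat-scan types, 2 of which also meet the continue sentence. In the worked record irPD moves by 28 days, or by 42 days or more, depending on which text is followed.

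Severity is minor. RECIST 1.1 endpoints and the primary safety objective are unaffected; the effect is on treatment decisions and on exploratory irRECIST analyses that use irPD, chiefly PFS. The size in patients is unknown and probably small. The day counts assume a first PD on day 43 and a repeat scan exactly 4 weeks later. Confidence is medium, because the unavailable guidance documents could already contain the missing rule.

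**What to change.** 1. Add an item to the confirmed-PD list in Protocol 8.1.1.3: *New unequivocal non-target progression since last evaluation.*
2. Rewrite the continue sentence as the complement of the list. Treatment may go on if the target increase is <20% or <5 mm versus nadir, causal non-target and new lesions are stable or improved, there is no additional new lesion, and there is no new unequivocal non-target progression. No repeat-scan type then meets both rules or neither.
3. In SAP 5.2.1.5, define confirmed and not confirmed by the Protocol 8.1.1.3 list, in place of the captions' consecutive and non-consecutive PD.

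The cost is one list item and one sentence in the protocol and two parentheticals in the SAP. No new data are needed, because target, non-target and new lesions are already part of each tumor assessment.

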8.1.4. Appropriateness of Measurements

The measures used in this study are consistent with those used in most conventional oncology trials.

8.2. Safety

Investigators are responsible for monitoring the safety of patients who have entered this study and for alerting Lilly or its designee to any event that seems unusual, even if this event may be considered an unanticipated benefit to the patient.

The investigator is responsible for the appropriate medical care of patients during the study.

The investigator remains responsible for following, through an appropriate health care option, AEs that are serious, considered related to the study, or that caused the patient to discontinue before completing the study. The patient should be followed until the event is resolved or explained. Frequency of follow-up evaluation is left to the discretion of the investigator.

The timing of all safety evaluations is shown in the Time and Events Table ([Attachment 1](#)).

[Table JVDF.7](#) presents a summary of AE and SAE reporting guidelines and shows which database or storage system is used.

Table JVDF.7. Adverse Event and Serious Adverse Event Reporting Guidelines

Period	Types of AEs/SAEs to be Reported^a	Collection Database^b	Lilly Safety System
Baseline (pretreatment)	Preexisting conditions	x	X
	All AEs	x	
	SAEs related to protocol procedures	x	
Study treatment period	All AEs	x	X
	All SAEs	x	
Short-term postdiscontinuation follow-up (30 days)	All AEs	x	X
	All SAEs	x	
Long-term postdiscontinuation period			
Through post-discontinuation follow-up visit (90 days)	All SAEs	x	X
Additional long-term discontinuation follow up (every 90 days to study completion)	All SAEs related to protocol procedures or IP	x	X
Continued access period	All AEs	x	X
	All SAEs	x	
Continued access follow-up (30 days; or sooner, to occur when patient begins a new anti-cancer therapy)	All AEs	x	X
	All SAEs	x	
After the patient is no longer participating in the study (that is, no longer receiving study treatment and no longer in follow-up)	All SAEs related to protocol procedures or IP that the investigator becomes aware of		X

Abbreviations: AEs = adverse events; CRF = case report form; IP = Investigational Product (ramucirumab or pembrolizumab); SAEs = serious adverse events.

a Although not strictly adverse events, pregnancy and breastfeeding are reported as SAEs. The reporting period starts after receiving IP(s) and ends 120 days after discontinuing study treatment or 30 days following cessation of treatment if the patient initiates new anticancer therapy, whichever is earlier.

b CRF collection guidelines will be followed.

8.2.1. Adverse Events

Lack of drug effect is not an AE in clinical trials, because the purpose of the clinical trial is to establish drug effect.

Any clinically significant findings from electrocardiograms (ECGs), labs, vital sign measurements, or other procedures that result in a diagnosis should be reported to Lilly or its designee.

After the informed consent form (ICF) is signed, study site personnel will record the occurrence and nature of each patient's preexisting conditions, including clinically significant signs and symptoms of the disease under treatment in the study. Site personnel will record the occurrence and nature of any AEs and any change in the preexisting condition(s). Progression of the cancer under study is not considered an adverse event unless it is considered to be drug-related by the investigator. All AEs related to protocol procedures are reported to Lilly or its designee.

In addition, all AEs occurring after the patient receives the first dose of IP must be reported to Lilly or its designee via CRF.

Investigators should report to Lilly or its designee their assessment of the potential relatedness of each AE to protocol procedure or IP via CRF.

The investigator decides whether he or she interprets the observed AEs as reasonably possibly related to disease, to the study regimen, study procedure, or other concomitant treatment or pathologies. To assess the relationship of the AE to the IP, the following is defined:

Reasonably Possibly Related: Reasonable possibility that there is a cause and effect relationship between the IP, study device, and/or study procedure and the AE.

The investigator answers yes/no when making this assessment.

Patients will be evaluated for AEs at each visit and will be instructed to call their physician to report any AEs between visits.

NCI-CTCAE v 4.0 will serve as the reference document for choosing appropriate terminology for, and grading the severity of, all AEs and other symptoms. For AEs without matching terminology within the NCI-CTCAE v 4.0 criteria, the investigator will be responsible for selecting the appropriate system organ class and assessing severity grade based on the intensity of the event.

In addition to collecting the AE verbatim and the CTCAE severity grade, AE verbatim text will also be mapped by Lilly or its designee to corresponding terminology within the Medical Dictionary for Regulatory Activities (MedDRA) dictionary.

If a patient's dosage is reduced or treatment is discontinued as a result of an AE, study site personnel must clearly report to Lilly or its designee via CRF the circumstances and data leading to any such dosage reduction or discontinuation of treatment.

8.2.1.1. Reporting Ramucirumab Adverse Events of Special Interest and Pembrolizumab Events of Clinical Interest

8.2.1.1.1. Infusion-Related Reactions-Ramucirumab and Pembrolizumab

Any treatment-related IRRs are defined according to the CTCAE Version 4.0 definition (*General Disorders and Administration Site Conditions*). Symptoms occurring during or following infusion of investigational therapy may also be defined according to AE categories such as allergic reaction, anaphylaxis, or cytokine release syndrome (*Immune System Disorders*). In the setting of symptoms occurring during or following infusion of investigational therapy, investigators are encouraged to use the AE term “infusion-related reaction” and any additional terms (including those not listed here) that best describe the event.

8.2.1.1.2. Adverse Events of Special Interest- Ramucirumab

Section [6.9.1.2.1](#) describes supportive care measures for each ramucirumab AESI.

[Table JVDF.3](#) presents the dose-modification guidelines for ramucirumab AESIs. Contact the Lilly CRP if questions arise concerning AESIs.

8.2.1.1.3. *Events of Clinical Interest- Pembrolizumab*

The 2 categories of ECIs include:

1. an overdose of pembrolizumab (≥ 1000 mg [5 times the dose]) not associated with clinical symptoms or abnormal laboratory results.
2. An elevated AST or ALT lab value that is greater than or equal to 3X the upper limit of normal (ULN) and an elevated total bilirubin lab value that is greater than or equal to 2X ULN and, at the same time, an alkaline phosphatase lab value that is less than 2X ULN, as determined by way of protocol-specified laboratory testing or unscheduled laboratory testing. Please refer to the Site Guidance Document for Drug-induced Liver Injury.

ECIs identified from the date of first dose through 90 days following discontinuation of study treatment, or 30 days after the initiation of a new anticancer therapy, whichever is earlier, need to be reported to the Sponsor (ECIs that are SAEs are reported within 24 hours, per Section 8.2.1.2).

8.2.1.2. **Serious Adverse Events**

An SAE is any adverse event from this study that results in one of the following outcomes:

- death
- a life-threatening experience (that is, immediate risk of dying)
- persistent or significant disability/incapacity
- initial or prolonged inpatient hospitalization
- congenital anomaly/birth defect
- considered significant by the investigator for any other reason, including, but not limited to:
 - Is a new cancer (that is, not a condition under study. NOTE: metastases are not considered to be a new cancer).
 - Is associated with an overdose (as defined in Section 8.2.1.1.3 for pembrolizumab and greater than the appropriate absolute dose based on the patient's weight as specified in Section 6.1.1).

Important medical events that may not result in death, be life-threatening, or require hospitalization may be considered serious adverse drug events when, based upon appropriate medical judgment, they may jeopardize the patient and may require medical or surgical intervention to prevent one of the outcomes listed in this definition.

Serious adverse event collection begins after the patient has signed informed consent and has received IP and ends 90 days following cessation of treatment, or 30 days following cessation of treatment if the patient initiates new anticancer therapy, whichever is earlier. If a patient experiences an SAE after signing informed consent, but prior to receiving IPs, the event will not be reported as serious unless the investigator feels the event may have been caused by a protocol procedure.

Study site personnel must alert Lilly or its designee of any **serious** adverse event (SAE) within 24 hours of investigator awareness of the event via a Sponsor-approved method. If study site

personnel contact Lilly or its designee by telephone regarding an SAE, study site personnel must also immediately provide official notification on study-specific SAE forms.

This 24-hour notification requirement refers to the initial SAE information and all follow-up SAE information.

Planned surgeries should not be reported as SAEs unless the underlying medical condition has worsened during the course of the study.

Planned hospitalizations or procedures for preexisting conditions that are already recorded in the patient's medical history at the time of study enrollment should not be considered SAEs.

Serious adverse events due to disease progression, including death, should not be reported unless the investigator deems them to be possibly related to the IPs.

The investigator does not need to actively monitor patients for AEs once the trial has ended, unless provided otherwise in the protocol; however, if an investigator becomes aware of an SAE occurring after the patient's participation in the trial has ended, and the investigator believes that the SAE is related to a protocol procedure or IPs, the investigator should report the SAE to the Sponsor, and the SAE will be entered in the Lilly Safety System.

Information on SAEs expected in the study population independent of drug exposure and that will be assessed by the Sponsor in aggregate periodically during the course of the trial may be found in the pembrolizumab and ramucirumab IBs.

